3.6.1 Enrolled Set

The Enrolled Set (ES) will consist form.

#### 3.6.2 **Safety Set**

The Safety Set (SS) will consist of all study participants in the ES who have received at least 1 dose of study medication.

#### 3.6.3 **Full Analysis Set**

The Full Analysis Set (FAS) will consist of all study participants in the SS who have no more than one of the 6 core components missing at baseline (count of joints with active arthritis, count of joints with limitation of range of motion, Physician's Global Assessment of Disease Activity score, CHAQ score, Parent's Global Assessment of Overall Well-Being score and CRP result) for calculating PedACR30/50/70/90.

## Pharmacokinetic Per-Protocol (PK-PP) Set 3.6.4

The Pharmacokinetic Per-Protocol (PK-PP) Set is a subset of the SS consisting of those study participants who took at least 1 dose of study medication, provided measurable plasma CZP concentration samples (with recorded sampling date/time or for which date/time can be reasonably assumed and it was analyzed using the ECLIA method) on at least 1 occasion. The PK-PP Set will be used for presentations of plasma concentration. The PK-PP Set was used for the PopPK model that was described in a separate data analysis plan (DAP) to support the marketing application in 2024.

### 3.7 Treatment assignment and treatment groups

All study participants received CZP as a fixed dose based on weight (Table 2–3). Prior to implementation of Protocol Amendments 4 and 5 (where study participants switched to the reduced dose), and after Protocol Amendment 9, the Original CZP Dose was followed; study participants in the 10 to <20kg weight group received CZP loading doses of 100mg and a maintenance dose of 50mg, study participants in the 20 to <40kg weight group received CZP loading doses of 200mg and a maintenance dose of 100mg, and study participants in the >40kg weight group received CZP loading doses of 400mg and a maintenance dose of 200mg, all Q2W. Following implementation of Protocol Amendments 4 and 5, all CZP doses were reduced by 50% (Reduced CZP Dose); study participants in the 10 to <20kg weight group received a CZP loading dose of 50mg Q2W and a maintenance dose of 50mg Q4W, study participants in the 20 to <40kg weight group received a CZP loading dose of 100mg Q2W and a maintenance dose of 50mg Q2W, and study participants in the >40kg

Confidential Page 29 of 252 weight group received a loading dose of 200mg Q2W and a maintenance dose of 100mg Q2W.

Prior to the implementation of Protocol Amendment 5, study participants were required to meet additional criteria prior to moving to a higher dosing category. Specifically, the following changes in weight were required prior to dose increases: (1) weight 40kg/88lb boundary due to a weight category (2) weight crosses the 20kg/87. 19.0kg study participant becomes 21.6kg).

For PK, safety and efficacy analyses, study participants will be grouped by their Baseline weight group. Selected analyses will also group study participants by their Baseline age group, concomitant MTX use, and ADAb titer (as defined in Section 8.2).

Regardless of specific prescribed doses dictated by weight change during study conduct, study participants will be analyzed by the CZP dose group stated in Section 3.1.

For analyses, all centers will be pooled together.

3.9

## Coding dictionaries

Adverse events and medical history will be coded using the Medical Dictionary for Regulatory Activities (MedDRA® version 23.1) according to UCB standard operating procedures (SOP). Medications will be coded using the World Health Organization Drug Dictionary (WHO-DD version dated Sep 2020 B3) according to UCB SOPs.

## Changes to protocol-defined analyses 3.10

The definition for the FAS has been clarified to the following: The Full Analysis Set (FAS) will consist of all study participants in the SS who have no more than one of the 6 core components (count of joints with active arthritis, count of joints with limitation of range of motion, Physician's Global Assessment of Disease Activity score, CHAQ score, Parent's Global Assessment of Overall Well-Being score and CRP result) for calculating improvement in PedACR30/50/70/90 missing at baseline.

are definition for the PK-PP has been clarified su have PK data analyzed using the ECLIA method.

In line with for the Understanding the ECLIA method. The definition for the PK-PP has been clarified such that study participants in this set must

response, for the Updated Week 24 Interim Analysis only, additional analyses were added to:

Confidential

- summarize exposure and treatment-emergent adverse events for when study participants were taking Complete Original CZP Dose and Complete Reduced CZP Dose.
  - Complete Original CZP Dose included all data for study participants who took
     Original CZP Dose prior to the first change in dosage as well as the data from when study participants increased their dosage to Original CZP after taking Reduced CZP Dose.
  - Complete Reduced CZP Dose included all data for study participants who took
     Reduced CZP Dose prior to the first change in dosage as well as the data from when
     study participants took Reduced CZP Dose after taking Original CZP Dose.
- summarize the proportion of study participants and the proportion of PK samples with sufficient volume for re-analysis with the ECLIA method out of all PK samples initially analyzed with the ELISA method were summarized by Original CZP Dose, Reduced CZP Dose, Complete Original CZP Dose, and Complete Reduced CZP Dose,
- summarize the proportion of study participants and the proportion of PK samples with sufficient volume for re-analysis with the ECLIA method out of all PK samples analyzed with the ECLIA method (either originally or via re-analysis) will be summarized by Original CZP Dose, Reduced CZP Dose, Complete Original CZP Dose, and Complete Reduced CZP Dose.
- summarize the proportion of study participants and the proportion of ADAb samples with sufficient volume for re-analysis with the ECLIA method out of all ADAb samples initially analyzed with the ELISA method will be summarized by Original CZP Dose, Reduced CZP Dose, Complete Original CZP Dose, and Complete Reduced CZP Dose.
- Additionally, to summarize the proportion of study participants and the proportion of ADAb samples with sufficient volume for re-analysis with the ECLIA method out of all ADAb samples analyzed with the ECLIA method (either originally or vis re-analysis) will be summarized by Original CZP Dose, Reduced CZP Dose, Complete Original CZP Dose, and Complete Reduced CZP Dose.

In the statistical section of the protocol, it is stated that the AEs will be summarized separately for the periods of exposure to Original CZP Dose and the Reduced CZP Dose, in addition to exposure for study participants that switched from the Reduced CZP Dose to the Original CZP Dose following Protocol Amendment 9. The analysis of AEs after a study participant changes doses will not be separately identified and presented in the Updated Week 24 Interim Analysis or the final analysis although the AEs that occur after dose changes will be summarized in the Any CZP Dose group.

In the statistical section of the protocol, it is stated that the frequency and percentage of AEs reported during the first 16 weeks of study medication exposure will be summarized separately for the 2 CZP doses (the Original CZP Dose, the Reduced CZP Dose), and that this analysis will be repeated, excluding any study participants who switched from the original to the reduced CZP dose prior to Week 16. The protocol-specified safety Week 16 analyses generated for prior interim analyses will not be included in the Updated Week 24 Interim Analysis or any later analyses.

Exposure-adjusted event rates (EAER) are added to selected TEAE tables.

This analysis plan, for the Updated Week 24 Interim Analysis only, includes plots of CZP plasma concentrations, ADAb titers, and maximum PedACR response for individual study participants by visit. Box plots of the PK distribution at Weeks 12 and 24 stratified by Baseline weight group, Baseline age group, concomitant MTX use and participant ADAb classification will be performed as a basis of the comparison with the adult RA PK exposures in RA0138; this comparison of observed PK data will be covered in Appendix Section 12.1. Plots of PK and ADAb data were not pre-specified in the study protocol.

It is not planned to perform a population PKPD modeling analysis of RA0043 data to explore the exposure-response relationship in pcJIA pediatric population for the following reasons: i) the purpose of the RA0043 study is to support the efficacy extrapolation to the pediatric population by PK matching with respect to RA adult PK, and thus the main aim of the analysis that will be performed by nonlinear mixed effect modeling is to characterize the PK in pcJIA pediatrics with precise parameter estimates; and ii) the W24 interim analyses performed and submitted in 2016 (BLA 125160-275) included PedACR and JADAS-71 graphical explorations by dose which concluded that a substantial improvement of the PedACR and JADAS-71 responses across both doses investigated in Study RA0043 was observed, with no differences between these, that would support a pop-PKPD analysis. Hence the PK-PD Set was removed as no analyses are planned for this population.

In the protocol it was stated that continuous efficacy endpoints would be presented using both last observation carried forward (LOCF) and observed case (OC) analyses. Instead, only observed case summaries of continuous efficacy endpoints will be presented since efficacy is not the primary objective of this study and little difference is expected between the two different analyses.

For the Updated Week 24 Interim Analysis, the efficacy data were summarized and plotted up to and including Week 24; all efficacy data were included in listings. For the Final Analysis, all data will be summarized and plotted, by visit (week) when there are 20 or more study participants with non-missing data, as applicable; all efficacy data will be included in listings.

For joints with limitation of motion (LOM), it was stated in the protocol that the assessment of LOM would be made using 69 of the 75 joints from the standard PRINTO/PRCSG standard joint examination. In all SAPs since SAP Amendment 2, the assessment now utilizes 67 joints and this was according to an updated definition of LOM in the PRINTO/PRCSG assessment that was not available prior to the finalization of the protocol.

For CRP, summaries present the percent change from Baseline instead of the ratio to Baseline to aid in interpretation.

## 4 STATISTICAL/ANALYTICAL ISSUES

## 4.1 Adjustments for covariates

No adjustment for covariates will be performed.

Confidential Page 32 of 252

## 4.2 Handling of dropouts or missing data

For all binary efficacy endpoints assessing response (PedACR30, PedACR50, PedACR70, PedACR90, CID, CRM), a study participant having missing data for the time point assessed will be conservatively counted as a non-remitter or non-responder. This will be done whether the data is missing, the study participant discontinued the study prior to the time point assessed, or the data is considered missing due to use of prohibited or rescue medication.

For all non-missed visits, if any of the PedACR core set measures are missing then those scores will be considered as not having met the criteria for improvement in the PedACR30, PedACR50, PedACR50, PedACR50 and PedACR90 response analyses. PedACR30, PedACR50, PedACR50, and PedACR90 responses will be derived if a single core set measure is missing. However, if 2 or more core set measures are missing, the corresponding PedACR30, PedACR50, PedACR50 and PedACR90 responses will in general be treated as missing.

Derived binary efficacy endpoints at visits affected by the use of rescue medications, or prohibited medications, will be treated as non-response. See Section 6.7 for a list of medications which would result in all efficacy data at only the next scheduled visit (and not all subsequent visits) being treated as missing/non-response. Any joint receiving intra-articular corticosteroids will be treated as missing with respect to assessments of that joint for 3 months (91 days).

For continuous efficacy endpoints, missing assessments will not be imputed.

For the non-responder imputation (NRI) calculations for binary efficacy outcomes,

- the study participants who discontinued up to and including Week 56, NRI will be imputed up to Week 56,
- the study participants who discontinued after Week 56, no imputation will be performed after the last visit,
- for study participants who take rescue and prohibited medications (see Section 6.6),
  - for visits up to and including Week 56, the outcomes are imputed as NRI up to Week
     56
  - for visits after Week 56, the outcomes are imputed as NRI if medication initiation is before or on Week 56
- for the initiation of rescue, short-acting or prohibited medications after Week 56, then the NRI imputation is not applied.

No further imputations of any other missing data are planned (eg, efficacy data missing at random).

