#### 6.6 **Rescue medications**

Rescue medication use is defined as any initiation of treatment or increase in dose of a medication used to treat pcJIA (in addition to the study drug) that is considered to impact the efficacy analyses. In general, a study participant requiring rescue medication after first administration of study drug is considered as a treatment failure from that time point forward for the purpose of efficacy analyses. Use of some short-acting medications (detailed below) may result in efficacy data at the next scheduled visit being treated as non-response (for categorical data).

A study participant requiring rescue medication may remain on study medication if the benefit/risk assessment of the study participant's continued participation is still favorable based on the Investigator's clinical assessment.

The use of rescue medication should be specifically avoided during the first 4 months (16 weeks) of treatment, if possible.

The following medications are defined as rescue medication in the first 16 weeks of this study:

- Initiation of MTX (if not being used at study entry), or increase of MTX above Baseline.
- Initiation of oral corticosteroids, or increase of oral corticosteroids above Baseline.

The following medications are defined as rescue medication when initiated in the first 56 weeks of the study:

- Initiation of MTX (if not being used at study entry), and increase of MTX above 15mg/m^2 per week at any time (based upon study participant's most recent body surface area [BSA] prior to an increase in MTX).
  - Initiation of oral corticosteroids, or increase to >10mg or 0.2mg/kg prednisone (or equivalent) per day (whichever is the smaller dose). A study participant's most recent weight prior to an increase of oral corticosteroids will be used to determine if the dosage increase meets the criterion.

BSA will be calculated using Mosteller's formula (Mosteller, 1987):

BSA (m^2) = 
$$\sqrt{\frac{\text{height (cm)} \times \text{weight (kg)}}{3600}}$$

The following medications are defined as rescue medication when initiated at any time up to Week 56 during the study:

- Injection of intra-articular (ia) corticosteroids into more than 2 joints at a single time point.

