- Injection of intra-articular (ia) corticosteroids into the same joint more frequently than 3 times in a 12-month (365 day) period. When such cases occur, the fourth injection within 12 months will be considered the time point at which rescue medication was initiated for the study participant.
- Intravenous (iv) corticosteroids (any dose), if not used for stress dosing for the purposes of surgery.
- Intramuscular (im) corticosteroids.

Any joint injected with ia corticosteroids will be excluded from the efficacy analysis for a period of 3 months (91 days).

In all cases, any medications recorded in the database will be classified as rescue medication only when pcJIA is listed as the indication for that medication. Rescue medication use and date of first usage will be confirmed during the data cleaning meetings prior to the database lock. Generally, the +1 day rule was applied to the first usage date when considering its impact on efficacy endpoints. Therefore, only efficacy data with dates after the first usage date of the rescue medication were impacted (using the non-responder imputation (NRI) method). The number and percentage of study participants who used rescue medication up to the Week 16 visit and after the Week 16 visit will be summarized separately.

All summaries of rescue medications will be provided for the SS for the Reduced CZP Dose, the Original CZP Dose and the Any CZP Dose. All rescue medication will be listed.

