## 10.3.2.1 Joints with active arthritis

The number of joints with active arthritis is the number of joints with:

- Grade 1 for swelling, or
- Grade 1 for LOM with POM, or
- Grade 1 for LOM with tenderness.

The count of joints with active arthritis is based on 71 of 75 joints from the PRINTO/PRCSG standard joint examination. Although 75 joints are included in the PRINTO/PRCSG standard joint examination, bilateral sacroiliac joints are not assessed for swelling or LOM and as a result are not included in the active arthritis count. Additionally, cervical, thoracic and lumbar joints are treated as a single composite joint in the computation of the number of joints with active arthritis. If 1 or more of these 3 spinal joints satisfy the criteria for joints with active arthritis, then the composite joint will be counted as a joint with active arthritis.

The assessment for swelling is made on 66 joints from the above list. The hip, subtalar, cervical spine, thoracic spine, lumbar spine, and sacroiliac joints are excluded. Artificial and ankylosed joints are excluded from both tenderness and swelling assessments. Joints treated with an intra-articular corticosteroid are also not assessed.

Eleven joints are not assessed for both LOM and swelling, and consequently active arthritis status will be based on the available partial assessments performed for those joints. Bilateral sternoclavicular and acromioclavicular joints are not assessed for LOM and as a result the

joints with active arthritis status will be based only on swelling. Conversely, bilateral hip and subtalar joints are not assessed for swelling and as a result active arthritis status will be based only on LOM. Cervical, thoracic and lumbar spine joints are also not assessed for swelling and as a result active arthritis status will be based only on LOM.

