In addition, joints with completely missing assessments that are otherwise expected to be evaluated will be treated as missing with respect to joints with active arthritis status. For example, MCP joints should be assessed for swelling, POM, tenderness and LOM at all visits. If all assessments for a given MCP joint are missing at a given visit, the joint will be treated as missing and will not be included as an assessed joint in the calculation of the active arthritis count. However, if partial data are available for a given joint, and the available data are sufficient to indicate that a given joint has active arthritis (eg, joint is assessed as swollen, but LOM and/or POM assessment is missing), the joint will be classified as a joint with active arthritis. However, if only partial data are available, and the partial data indicate that the joint is unaffected, the joint will also be treated as missing for the determination of the number of joints with active arthritis at that time point.

The active arthritis count will be weighted by the number of joints assessed:

$$AAC = \frac{71 * \sum_{i=1}^{n} JAA}{\sum_{i=1}^{n} JA}$$

where AAC=active arthritis count, JAA=number of joints with active arthritis, and JA=number of joints assessed. If more than 50% of the joints are not assessed, then the count of joints with active arthritis will be set to missing.

The number of joints with active arthritis and change from Baseline in number of joints with active arthritis will be summarized (observed case) for every visit except the Final Visit.

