### 10.3.9.2 Final Analysis

A study participant will be considered to be in CID at a given point in time if they meet all of the following criteria:

- No joints with active arthritis: based upon both (1) a "No" response to the question "Has the subject experienced any of the following since the last visit Joint(s) with active arthritis?", and 0 joints with active arthritis at the current visit
- No fever, rash, serositis, splenomegaly, or generalized lymphadenopathy attributable to JIA: based upon a "No" response to the question "Has the subject experienced any of the following since the last visit Fever, rash, serositis, splenomegaly, or generalized lymphadenopathy attributable to JIA?"
- No active uveitis as defined by the Standardization of Uveitis Nomenclature Working Group: based upon a "No" response to the question "Has the subject experienced any of the following since the last visit Active uveitis as defined by the Standardization of Uveitis Nomenclature Working Group?"
- CRP within normal limits in the laboratory where tested or, if elevated, not attributable to JIA: based upon a "No" response to the question "Has the subject experienced any of the following since the last visit Elevated CRP levels attributable to JIA?"
- Physician's Global Assessment of Disease Activity score of best possible on the scale used (ie, 0mm on the 100mm VAS): based upon VAS score at current visit

Duration of morning stiffness of ≤15 minutes: based upon duration of morning stiffness at current visit

The 6 criteria above will be used to derive CID. If any of the 6 criteria cannot be assessed due to missing data, the study participant will be assumed not to have achieved derived CID at the corresponding visit.

Derived CID will be assessed at every post-Baseline visit except the Final Visit.

The n and percentage of study participants with derived CID will be summarized for each post-Baseline visit. The exact 95% CI for the percentage will also be presented.

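### For 91 days after a non-rescue intra-articular injection, the joint counts omit the injected joint while Baseline keeps it, so PedACR, JADAS-71 and CID can look better than the joints are

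*SAP*

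**What the plan says.** Three places in the SAP remove an injected joint. Section 4.2 has the rule "Any joint receiving intra-articular corticosteroids will be treated as missing with respect to assessments of that joint for 3 months (91 days"). Section 6.6 repeats it: "Any joint injected with ia corticosteroids will be excluded from the efficacy analysis", for the same period. Section 10.3.2.1 adds "Joints treated with an intra-articular corticosteroid are also not assessed".

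The counts are then rescaled. In 10.3.2.1, "The active arthritis count will be weighted by the number of joints assessed": 71 × active joints / joints assessed. Section 10.3.2.2 does the same for LOM with 67. Either count becomes missing only when more than half of the joints are unassessed. Section 10.3.2 removes a joint from all visits only if it could not be evaluated at Baseline, so a joint injected later stays in the Baseline count.

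Whether non-response follows depends on 6.6. Up to Week 56, rescue includes "Injection of intra-articular (ia) corticosteroids into more than 2 joints at a single time point" and a fourth injection of the same joint within 365 days. One or two joints per session is not rescue, and intra-articular steroid is not among the short-acting medications in 6.7. After Week 56 no intra-articular injection is defined as rescue, and 4.2 applies no non-responder imputation to rescue started then.

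The counts are two of the six PedACR core measures (10.2) and the active count is a component of JADAS-71 (10.3.8). Derived CID (10.3.9.2) requires, among other items, "0 joints with active arthritis at the current visit", and derived CRM is built on CID (10.3.10.2).

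**The concern.** Joints are normally injected because they are active, so removing them is informative. At the post-injection visit the joint is given the average status of the joints left in, which is mostly unaffected, while the reference value at Baseline still counts it as affected. The difference appears as improvement although no other joint has changed.

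This reaches the secondary efficacy variable, PedACR at Week 16 (2.2.2). A non-rescue injection at Week 4 opens a window that closes on day 28 + 91 = 119, that is Week 17, so the visits at Weeks 8, 12 and 16 all fall inside it. The study is open-label. Other concomitant treatment is handled more strictly: an above-Baseline analgesic within 48 hours of a visit makes that visit missing or non-response (6.7), whereas steroid into two active joints leaves the visit evaluable and can improve its score.

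**Working it through.** **Denominators.** The SAP says "The count of joints with active arthritis is based on 71 of 75 joints from the PRINTO/PRCSG" examination. Check: 75 − 2 sacroiliac − 2 (three spinal joints merged into one) = 71. For LOM: 71 − 2 sternoclavicular − 2 acromioclavicular = 67. Both agree with the plan.

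**Formula.** Let T be the denominator (71 or 67), a the affected joints and k the number of those injected. Then

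count = T(a − k)/(T − k) = (a − k) + k × (a − k)/(T − k).

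Each injected joint thus contributes (a − k)/(T − k), the mean of the assessed joints. With a = 5, k = 2 this is 3/69 = 0.043 for active arthritis and 3/65 = 0.046 for LOM, in place of 1.

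**Joints affected at Baseline, all non-injected joints unchanged.** The entry minimum is 5 active joints (2.3).

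| Count | Affected at Baseline | Injected | Count inside window | Apparent improvement |
|---|---|---|---|---|
| Active | 5 | 2 | 71 × 3/69 = 3.09 | 38.3% |
| LOM | 5 | 2 | 67 × 3/65 = 3.09 | 38.2% |
| Active | 6 | 2 | 71 × 4/69 = 4.12 | 31.4% |
| Active | 7 | 2 | 71 × 5/69 = 5.14 | 26.5% |
| Active | 10 | 2 | 71 × 8/69 = 8.23 | 17.7% |
| Active | 5 | 1 | 71 × 4/70 = 4.06 | 18.9% |
| Active | 10 | 4 | 71 × 6/67 = 6.36 | 36.4% |

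Two injections alone pass 30% on a count when its Baseline value is 6 or less; one injection does so at 3 or less. The last row can arise before Week 56 from two sessions of two different joints within 91 days, or after Week 56 from a single session.

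**Added to real improvement.** Baseline 6 active, 4 still active: 1 − 4/6 = 33.3%. If 2 of those 4 are injected, 71 × 2/69 = 2.06, or 65.7%, which passes the 50% threshold on that item.

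**Joint not active at Baseline.** Five Baseline joints persist and two new ones flare and are injected: 71 × 5/69 = 5.14 (+2.9%), against 7 (+40%) if the new joints were counted.

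**JADAS-71.** In the 5-joint case the total is lower by 5 − 3.09 = 1.91 points.

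**CID.** If the only two active joints are both injected, 71 × 0/69 = 0.

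**Reference.** Counting the injected joints as affected leaves the 5-joint case at 5.00 (0% change). Removing the same two joints from Baseline as well also gives 0%.

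**The case against.** The strongest reply is that this is a deliberate, uniform rule: every unassessed joint is rescaled in the same way, and excluding an injected joint is slightly stricter than using its reading after steroid has quieted it (3.09 against 3.00). That is correct. The favourable shift is relative to keeping the joint as affected, not to the observed post-steroid reading.

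Several stronger readings that a reader might infer are not supported:

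- *The count always falls.* It falls only when the injected joint would otherwise be scored affected. An injected joint without LOM slightly raises the LOM count, and a joint inactive at Baseline has its worsening hidden without any improvement being shown.
- *Injection creates a PedACR response.* Three core items are needed and the counts are two. Larger sessions and fourth injections up to Week 56 are scored as non-response.
- *The rule contradicts the conservative handling in 4.2.* That principle covers missing binary responses and missing core measures; the joint-level rule stands beside it as a separate choice.
- *CID is granted by injection.* CID also requires a negative answer on active joints since the last visit, a Physician's Global of 0 mm, and the CRP, morning-stiffness, uveitis and systemic-feature items. A gap remains at a second visit inside the window. With 8-week visits, an injection up to 91 − 56 = 35 days before one visit leaves the next visit inside the window but outside the recall of that question.
- *Response rates are materially inflated.* The SAP gives no injection frequency.

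Efficacy is not primary and no hypothesis is tested. The Updated Week 24 Interim Analysis has already used the current counts, so replacing the main derivation would break comparability. Concomitant intra-articular injections are tabulated (6.4), but that table does not show whether they coincide with response.

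**Conclusion.** The concern holds in limited form. For non-rescue injections (one or two joints per session up to Week 56, any number afterwards), the rescaled counts set a follow-up value without the injected joint against a Baseline that includes it. For joints active at Baseline and a low Baseline count, this can supply up to two of the three items for PedACR30: 38% on each count with 5 joints and 2 injected. The effect shrinks to about 18% with 10 joints and 2 injected. It also lowers JADAS-71 and can produce the zero count that CID requires; for newly active joints it conceals worsening.

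The figures assume that the injected joints would otherwise count as affected, that all other joints are unchanged and, for the two-item case, that the injected joints are also limited in motion. These are participant-level illustrations. The effect on group response rates cannot be computed from the document.

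**What to change.** Amend 4.2, 10.3.2.1, 10.3.2.2 and 10.3.9.2 as follows.

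1. Keep the present derivation of the counts, PedACR and JADAS-71 as the main one, for continuity with the Updated Week 24 Interim Analysis.
2. Add a prespecified sensitivity analysis of PedACR30/50/70/90 (including Week 16), both joint counts and JADAS-71. In it, every joint injected after Baseline counts as affected for 91 days (active, and limited in motion where LOM is assessed for that joint) and stays in the number of joints assessed.
3. Do not carry forward the joint's status from the last visit. SAP Amendment 4 removed last-observation-carried-forward at FDA's suggestion. Carry-forward would also score a joint that flared and was injected between visits as unaffected: with 5 other active joints and 2 such injections the count would be 71 × 5/71 = 5.00, more favourable than the present 5.14.
4. For derived CID, and so for derived CRM, do not accept a zero joint count while any joint is inside its 91-day window. The interim analysis only listed CID and CRM, so no summarised result is disturbed.

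The cost is one additional derivation on data already collected, and somewhat less favourable supplementary results and CID/CRM figures. Counting the joint as affected is deliberately cautious, so the two versions show how far the injections matter.
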